3.1 Definitions

The following definitions apply:

- Baseline: The latest non-missing observation prior to first treatment with IMP.

Baseline data definition	obtained on/at
Age, race, height, body weight, BMI	Screening
Relevant medical history (last 5 years) including psoriasis history, relevant surgical history (last 5 years) and relevant previous medication (last 6 weeks) including psoriatic treatment taken (last 6 weeks)	Screening
Smoking and alcohol consumption	Screening
Concomitant medication	Day 1
Adverse events	Day 1
Physical examination	Day 1, Screening*
Vital signs (blood pressure, pulse rate)	Day 1, Screening*
Safety laboratory parameters	Day 1, Screening*
PASI, PGA, BSA	Day 1, Screening*

*only in case of missing Day 1 assessment

- Change from baseline = post baseline value – baseline value
- Percent change from baseline = $100 * \text{change from baseline} / \text{baseline value}$
- Last observation carried forward (LOCF): The last observed value (either scheduled or unscheduled) carried forward and used for all directly subsequent and missing scheduled points.
- Current medical conditions – medical conditions ongoing at first dosing.
- Prior therapy: Any medication or therapy taken prior to start of first IMP dosing.
- Concomitant therapy: A medication or therapy ongoing at start of first IMP dosing, or starting after the first IMP dosing.
- Treatment emergent adverse event (TEAE): Adverse event with an onset (or worsening) on or after the time of the first IMP dosing.
- Time to achievement of PASI 50 (75): Day of first visit were PASI 50 (75) is observed.
- Analysis centers: Pooled small centers for analyses, as described in section 3.5.4.

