3.4.6.2 Statistical analyses

Primary efficacy endpoints

The co-primary endpoint response in PASI 75 at Week 12 (Day 84) is defined as 75% improvement in PASI score compared to baseline (i.e. percent of change from baseline $\leq 75\%$). The co-primary endpoint improvement in PGA at Week 12 (Day 84) is defined as reduction by 1 or more points on the PGA scale in comparison to baseline.

The comparisons of the treatment groups MP1032 300 mg bid and MP1032 150 mg bid, each vs. the placebo treatment, with respect to each, the PASI 75 rate and PGA improvement rate, at Week 12 (Day 84) will be evaluated by the CMH test stratified by (pooled) analysis center. The common odds-ratio with 95% confidence interval will be provided. The homogeneity of the individual odds-ratios will be assessed by the Breslow-Day test.

Secondary efficacy endpoints

Secondary efficacy endpoints will be evaluated descriptively. The methodology outlined at the top of this section 3.4.6.2 will be applied for pairwise treatment comparisons vs. placebo:

The PASI 50 responder rate at Week 12 (Day 84) will be evaluated according to the primary efficacy endpoints, as well as the PASI 75, PASI 50 and PGA improvement at Week 4 (Day 28) and Week 8 (Day 56) of the treatment phase and at follow-up, 4 weeks after end of treatment.

The change in the PASI score from baseline to each post baseline visit, respectively, will be evaluated using an analysis of covariance (ANCOVA) model, with treatment group and (pooled) analysis center as factors and baseline outcome as covariate, in both analysis sets, FAS and VCS.

The time to achievement of PASI 50 and PASI 75, respectively, will be evaluated using the Kaplan-Meier method. The study day of first achievement of PASI 50 and PASI 75, respectively, will be the considered event, with study day of last assessment as the time point of censoring, in case of no occurrences of PASI 50 or PASI 75. Pairwise treatment group differences will be tested by the log-rank test.

Location shift in change from baseline in PGA will be assessed using Hodges-Lehmann Estimation with comparison by the Wilcoxon rank sum test, in both analysis sets, FAS and VCS.

Descriptive summaries will be provided for each parameter by treatment group and by visit, if applicable. Percentages will be provided based on the number of non-missing cases, if not otherwise stated. For PASI and PGA the descriptive summaries will be performed in both analysis sets, FAS and VCS.

Subgroup analyses

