3.5.2 Window for time points

A strict adherence to the visit schedule will be required. Visit schedule violations will be documented as protocol deviations and assessed within the BDRM.

Assessments performed out of the planned visit schedule will be assigned to the nearest, directly preceding or following planned visit, if that visit is missing. If both planned visits are missing and the distances are equal, the assignment is performed to the following one. Otherwise an assessment performed out of the planned visit schedule will not be included in the statistical evaluation and will be listed only.

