Withdrawal by subject	XX (XXX.X%)	XX (XXX.X%)	XX (XXX.X%)	XX (XXX.X%)
Other	XX (XXX.X%)	XX (XXX.X%)	XX (XXX.X%)	XX (XXX.X%)

EoT: End of treatment.

¹ Week 12/EoT visit of PASI within the time range 80 ≤ study day ≤ 91 and exposure ≥ 80% planned exposure

² Week 12/EoT visit of PASI at a study day ≤ 79 or exposure < 80% planned exposure

Source data: <DATASET> <DATE>

Program: <SAS PROGRAM> <DATE>

Table 14.1.4: Excluded subjects from the analysis populations (Randomized subjects)
(Part 1 of 1)

	MP1032 300 mg bid	MP1032 150 mg bid	Placebo bid	Total
Number of randomized subjects	N = XX	N = XX	N = XX	N = XX
Subjects excluded from the SES	XX (XXX.X%)	XX (XXX.X%)	XX (XXX.X%)	XX (XXX.X%)
Primary exclusionary reason / protocol deviation ¹				
Subject did not receive any IMP	XX (XXX.X%)	XX (XXX.X%)	XX (XXX.X%)	XX (XXX.X%)
Subjects excluded from the FAS	XX (XXX.X%)	XX (XXX.X%)	XX (XXX.X%)	XX (XXX.X%)
Primary exclusionary reason / protocol deviation ¹				
Subject did not receive any IMP	XX (XXX.X%)	XX (XXX.X%)	XX (XXX.X%)	XX (XXX.X%)
Subject has no post-baseline assessment	XX (XXX.X%)	XX (XXX.X%)	XX (XXX.X%)	XX (XXX.X%)
Subjects excluded from the VCS	XX (XXX.X%)	XX (XXX.X%)	XX (XXX.X%)	XX (XXX.X%)
Primary exclusionary reason / protocol deviation ¹				
Subject did not receive any IMP	XX (XXX.X%)	XX (XXX.X%)	XX (XXX.X%)	XX (XXX.X%)
Subject has no post-baseline assessment	XX (XXX.X%)	XX (XXX.X%)	XX (XXX.X%)	XX (XXX.X%)
Subject took interfering concomitant medication	XX (XXX.X%)	XX (XXX.X%)	XX (XXX.X%)	XX (XXX.X%)
Subject did not complete Week 12 visit (EoT)	XX (XXX.X%)	XX (XXX.X%)	XX (XXX.X%)	XX (XXX.X%)
Subject not compliant with dosing regimen ²	XX (XXX.X%)	XX (XXX.X%)	XX (XXX.X%)	XX (XXX.X%)
Other major protocol deviations	XX (XXX.X%)	XX (XXX.X%)	XX (XXX.X%)	XX (XXX.X%)
Subjects excluded from the PKS	XX (XXX.X%)	XX (XXX.X%)	XX (XXX.X%)	XX (XXX.X%)
Primary exclusionary reason / protocol deviation ¹				
Subject did not receive any IMP	XX (XXX.X%)	XX (XXX.X%)	XX (XXX.X%)	XX (XXX.X%)
Subject has no completed determination of MP1032 levels	XX (XXX.X%)	XX (XXX.X%)	XX (XXX.X%)	XX (XXX.X%)
Subject took interfering concomitant medication	XX (XXX.X%)	XX (XXX.X%)	XX (XXX.X%)	XX (XXX.X%)
Other major protocol deviations	XX (XXX.X%)	XX (XXX.X%)	XX (XXX.X%)	XX (XXX.X%)

¹ In case of multiple deviations, only the primary exclusionary reason / protocol deviation is counted;

² Subjects who had less than 80% of the expected oral doses.

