PASI 75¹ – LOCF	MP1032 300 mg bid (N = XX)	MP1032 150 mg bid (N = XX)	Placebo bid (N = XX)
Week 16 / Follow up			
N	XX	XX	XX
Responder	XX (XXX.X%)	XX (XXX.X%)	XX (XXX.X%)
Non-responder	XX (XXX.X%)	XX (XXX.X%)	XX (XXX.X%)
Comparison vs Placebo ²			
p-value	X.XXX	X.XXX	--
Odds ratio	X.XX	X.XX	--
Confidence interval	X.XX, X.XX	X.XXX	--
Breslow-Day test ³	X.XXX	X.XXX	--

¹ 75% improvement in PASI score

² Cochran-Mantel-Haenszel (CMH) test: p-value for the hypothesis, that all within-stratum odds ratios equal to 1 and estimate of the common odds ratio with 95% confidence interval

³ p-value of Breslow-Day test for the hypothesis that all individual odds-ratios are equal

Source data: <DATASET> <DATE>
Program: <SAS PROGRAM> <DATE>

Table 14.3.4: PASI – PASI 50 responders – LOCF (FAS)
Analog to Table 14.3.3 for PASI 50

Table 14.3.5: PASI – Time to PASI 75 (FAS)
(Part 1 of 1)

Time to PASI 75	MP1032		MP1032		Placebo bid	
	300 mg bid (N = XX)	150 mg bid (N = XX)	150 mg bid (N = XX)	Placebo bid (N = XX)	Placebo bid (N = XX)	
Week 4	PASI 75 reached XX (XXX.X%)	Censored XX (XXX.X%)	PASI 75 reached XX (XXX.X%)	Censored XX (XXX.X%)	PASI 75 reached XX (XXX.X%)	Censored XX (XXX.X%)
Week 8	XX (XXX.X%)	XX (XXX.X%)	XX (XXX.X%)	XX (XXX.X%)	XX (XXX.X%)	XX (XXX.X%)
Week 12/ EoT	XX (XXX.X%)	XX (XXX.X%)	XX (XXX.X%)	XX (XXX.X%)	XX (XXX.X%)	XX (XXX.X%)
Week 16 / Follow up	XX (XXX.X%)	XX (XXX.X%)	XX (XXX.X%)	XX (XXX.X%)	XX (XXX.X%)	XX (XXX.X%)
Kaplan-Meier estimator (95%-CI) ¹	XX (XX, XX)		XX (XX, XX)		XX (XX, XX)	
Comparison vs Placebo (Log-rank test p-value)	X.XXXX		X.XXXX		--	

¹ Kaplan-Meier estimate of the median time [day] to reach the PASI 75 criterion. The study day of first achievement of PASI 75 considered, with study day of last assessment as the time point of censoring, in case of no occurrences of PASI 75.

Source data: <DATASET> <DATE>
Program: <SAS PROGRAM> <DATE>

Table 14.3.6: PASI – Time to PASI 50 (FAS)
Analog to Table 14.3.5 for the time to achieve PASI 50

Table 14.3.7: PASI – ANCOVA for change from baseline – LOCF (FAS)
(Part 1 of 2)

PASI changes from baseline	MP1032 300 mg bid (N = XX)	MP1032 150 mg bid (N = XX)	Placebo bid (N = XX)
Week 4			
N	XX	XX	XX
Mean \pm SE ¹	XX.X \pm XX.X	XX.X \pm XX.X	XX.X \pm XX.X
95%-CI ¹	XX.X , XX.X	XX.X , XX.X	XX.X , XX.X
Comparison vs Placebo			
Estimate \pm SE ¹	XX.X \pm XX.X	XX.X \pm XX.X	--
95%-CI ¹	XX.X , XX.X	XX.X , XX.X	--
p-value ¹	X.XXX	X.XXX	--
Week 8			

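### Time to PASI 50/75 is timed by each patient's own study day, which inflates the last Kaplan-Meier step when Week 16 visits are scattered and can yield a median in an arm where fewer than half responded

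*SAP*

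**What the plan says.** SAP 3.1 defines the time to response as "Day of first visit were PASI 50 (75) is observed". SAP 3.4.6.2 carries this into the Kaplan-Meier analysis: "The study day of first achievement of PASI 50 and PASI 75, respectively, will be the considered event". Patients who never respond are dealt with in the same sentence and leave the analysis at their own final examination, "with study day of last assessment as the time point of censoring, in case of no occurrences of PASI 50 or PASI 75". Footnote 1 of Table 14.3.5 in the SAP Appendix repeats the rule and names the statistic to be printed, the "Kaplan-Meier estimate of the median time [day] to reach the PASI 75 criterion", with a 95% CI. Table 14.3.6 is built the same way for PASI 50.

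Three further places settle how the rule works in practice:

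- Study day is patient-specific. A footnote to Table 14.1.3 describes a "Week 12/EoT visit of PASI within the time range 80 ≤ study day ≤ 91", so the term does not mean the nominal Day 84.
- Week 16 belongs to the analysis. Table 14.3.5 has a row for "Week 16 / Follow up", and the flow chart in SAP 2.3 gives that visit as Day 112 with a window of 2 days either side.
- SAP 3.5.2 says that an off-schedule assessment "will be assigned to the nearest, directly preceding or following planned visit, if that visit is missing". That rule labels the assessment with a visit. It does not replace the day on which it took place.

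Neither document specifies nominal days, an interval-censored or discrete-time method, or a cut-off at Week 12 for this endpoint.

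**The concern.** Response can be seen only at four scheduled visits, unscheduled assessments aside. A patient examined at Week 16 without response is a known non-responder at Week 16. Under the SAP rule, if that patient attends on Day 110 and another patient first responds on Day 114, Kaplan-Meier treats the first as having unknown status after Day 110. It passes that patient's weight to those who attended later. The risk set shrinks within one planned visit while events of that visit are still being counted, so the estimated proportion responding at that visit is too high. Scheduling within a five-day window moves the curve, not response. This affects completers with full follow-up, in any arm.

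At stake is the median time to response, the only Kaplan-Meier estimate in Tables 14.3.5 and 14.3.6. Because the distortion sits at the end of the curve, it can carry an arm past 50% when fewer than half of its patients responded.

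**Working it through.** **The plan's figures.** The documents give no expected value for this endpoint. Their one computed figure is in SAP 2.2: 40 per group for rates of 0.674 and 0.40, two-sided alpha 0.10, 80% power. It reproduces: (1.645·√(2·0.537·0.463) + 0.842·√(0.24 + 0.2197))² / 0.274² = 39.9, rounded up to 40. The rates 40% and 67.4% are borrowed below as illustrations of Week 12 response.

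**Inputs.**
- From the documents: 50 patients per arm (SAP 2.1), 40 evaluable per arm and hence 20% loss (SAP 2.2), Week 16 on Days 110 to 114 (SAP 2.3).
- Assumed: how visits are spread within the window, and q, the chance of a first response at Week 16 among those still at risk.

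The Day 84 window is +5 days in the protocol flow chart and ±5 in the SAP. This does not enter the Week 16 step.

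**Worked record.** Take 50 patients, 20 responding by Week 12, so S = 0.60. The other 30 attend six per day on Days 110 to 114. The numbers at risk are then 30, 24, 18, 12 and 6.
- First responses on Days 113 and 114: S = 0.60 × 11/12 × 5/6 = 0.458. Kaplan-Meier shows 54% and a median of Day 114; the observed proportion is 22/50 = 44%.
- One first response, on Day 114: S = 0.60 × 5/6 = 0.50. Kaplan-Meier shows 50%; the observed proportion is 21/50 = 42%.
- First responses on Days 110 and 111: S = 0.60 × 29/30 × 23/24 = 0.556, or 44.4%, close to the true 44%.
- Both on Day 112: S = 0.60 × 16/18 = 0.533, or 46.7%.

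Two responders can be placed among the 30 patients in 435 ways. S falls below 0.5 when at least one is on Day 114: 6 × 24 + 15 = 159 ways, or 37%. Adding the 15 exact ties (both on Day 113) makes 40%.

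**Size of the step.** With share f_j of the at-risk patients seen on day j and share R_j not yet seen, the Week 16 factor in a large sample is ∏(1 − q·f_j/R_j). On nominal days it is 1 − q. For an even spread and small q the inflation is (1/5)(5/5 + 5/4 + 5/3 + 5/2 + 5/1) = 2.28. For q = 0.10 the factor is 0.98 × 0.975 × 0.9667 × 0.95 × 0.90 = 0.790. From S = 0.60 this gives 0.474 and a median of Day 114. Nominal days give 0.540 and no median.

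| Spread within Days 110–114 | Inflation of the step, q from 0.02 to 0.30 |
|---|---|
| Even | 1.78–2.25 |
| Triangular | 1.91–2.48 |
| 60% on Day 112 | 2.02–2.66 |
| 80% on Day 112 | 2.05–2.69 |
| 90% on Day 112 | 1.69–1.98 |
| All on Day 112 | 1.00 |

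**How often a median appears that nominal days would not give.** Both rules were applied to the same simulated arms: 1,500 per setting, n = 40 or 50, dropout 0 or 20%, even spread or 60% on Day 112. A curve at exactly 50% counts as reached. Without dropout, such a median means that fewer than half responded.

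| Assumed cumulative response, Week 12 → Week 16 | Arms affected |
|---|---|
| 10% → 12% | 0.1–2% |
| 15% → 20% | 1–8% |
| 30% → 35% | 14–18% |
| 40% → 43% | 10–18% |
| 40% → 45% | 16–29% |
| 67.4% → 70% | about 0% |
| 40%, none new at Week 16 | 0% without dropout, about 2% with 20% |

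**The case against.** The strongest reply is that the consequence is conditional. A spurious median needs first responses at Week 16, four weeks after dosing ends, and usually a Week 12 response not far below one half. The two-responder record that gives 54% puts both on the last two days, and about 60% of placements give no median. Even on nominal days a finite median appears in some arms whose underlying rate is below 50%, through ordinary sampling. SAP 3.5.2 demands close adherence to the visit schedule, and if everyone came on Day 112 the inflation would vanish. All of this stands. It limits how often harm occurs, not whether the estimator is wrong: with 90% of visits on Day 112, the step is still inflated about 1.7 to 2.0 fold.

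It is also true that Table 14.3.5 prints counts of patients reaching response and censored at each visit, above the median, and that Tables 14.3.3 and 14.3.4 give responder rates by visit. An attentive reader could notice 44% responding beside a median of Day 114. That softens the harm but leaves a table that contradicts itself.

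A reader might infer that the comparison with placebo is biased. The documents do not support that. SAP 3.4.6.2 compares arms by the log-rank test, not by medians, and the distortion arises in every arm. A simulation with 50 per arm and assumed hazards gave rejection under no effect of 4.9% on actual days and 5.1% on nominal days. Power in one assumed scenario was 46.4% and 45.9%.

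**Conclusion.** The point holds as a flaw in a reported secondary estimate. The SAP's definitions make known Week 16 non-responders leave the risk set before other Week 16 events. If visits are scattered and there are first responses at Week 16, the last step is inflated about 1.7 to 2.7 fold.

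A median in an arm with fewer than half responding is a risk, not a certainty. It is material for PASI 50 or for any arm near 30 to 40% at Week 12 (roughly 10 to 29% of arms near 40%). At low PASI 75 rates it is mostly a few percent or less, with 8% the highest value in the settings tried. It is essentially nil where the median is reached by Week 12.

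The mechanism follows from the text; the frequencies rest on the assumed spread of visits and Week 16 response. It would go too far to say that the rule always creates false medians, or that it harms the log-rank test or the primary CMH analyses. The trial is exploratory and this endpoint is descriptive, so the correction is worth making but is not critical.

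**What to change.** In SAP 3.1, SAP 3.4.6.2 and the footnotes of Tables 14.3.5 and 14.3.6, define event and censoring times by planned visit (Day 28, 56, 84 or 112), using the visit to which SAP 3.5.2 assigns the assessment. State that events are counted before censorings tied at the same time. The Week 16 step then equals the observed proportion among those at risk.

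In both shells, add the Kaplan-Meier cumulative proportion with 95% CI at each planned visit, beside the median. No extra rule for when to show the median is needed, since a Kaplan-Meier median exists only where the curve reaches 50%.

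The cost is SAP wording and two shell edits, with no new data. The small downside is that the median can take only the four planned visit days, which is all the schedule can resolve.

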1.2 Objectives

The trial is designed with two primary endpoints as described in the EMA guideline [2].

Table 1 Objectives and endpoints:

Primary objective	Primary endpoint
The primary objective of this trial is to evaluate the clinical efficacy and safety of two oral doses of MP1032 (150 mg bid and 300 mg bid) when taken for 12 weeks by patients with moderate-to-severe chronic plaque psoriasis.	
Efficacy: MP1032 300 mg bid vs. placebo
 
1.1 Percentage of patients who achieve a 75% improvement (response) in their PASI score (PASI 75) at Week 12 (Day 84) compared to baseline in patients treated with 300 mg bid of MP1032 compared to placebo
 
1.2 Improvement (1 or more points on a 7 Point Scale) in PGA at Week 12 (Day 84) compared to baseline in patients treated with 300 mg bid of MP1032 compared to placebo
 
Efficacy: MP1032 150 mg bid vs. placebo
 
2.1 Percentage of patients who achieve a 75% improvement (response) in their PASI score (PASI 75) at Week 12 (Day 84) compared to baseline in patients treated with 150 mg bid of MP1032 compared to placebo
 
2.2 Improvement (1 or more points on a 7 Point Scale) in PGA Score at Week 12 (Day 84) compared to baseline in patients treated with 150 mg bid of MP1032 compared to placebo
 
Safety:
 
3 Incidence of adverse events

Secondary objectives	Secondary endpoints
To evaluate the effect of each oral doses of MP1032 (150 mg bid and 300 mg bid) compared to placebo on the PASI score	
 Percentage of patients who achieve a 50% improvement (response) in their PASI score (PASI 50) at Week 12 (Day 84) compared to baseline in patients treated with 300 mg bid of MP1032 compared to placebo Percentage of patients who achieve a 50% improvement (response) in their PASI score (PASI 50) at Week 12 (Day 84) compared to baseline in patients treated with 150 mg bid of MP1032 compared to placebo Mean PASI score and change from baseline at Week 4 (Day 28), 8 (Day 56), 12 (Day 84) and week 16 (Day 112) Time to achieve PASI 50 and PASI 75
To evaluate the effect of each oral dose of MP1032 (150 mg bid and 300 mg bid) compared to placebo on the PGA score	
 Mean score and change from Baseline at Week 4 (Day 28), 8 (Day 56), 12 (Day 84) and 16 (Day 112) in the PGA

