The following subgroups, based on baseline parameter, will be evaluated with respect to the primary efficacy variables PASI and PGA for each post-baseline visit within the FAS:

Table 4 Subgroups

Center:	• Analysis (pooled) centers		
Age:	• 18 to 40	• >40	
Sex:	• Male	• Female	
BMI:	• ≤ 24.9 (normal)	• 25.0 - 29.9 (pre-obesity)	• ≥ 30.0 (obesity)
Years of psoriasis:	• 1 to 10	• >10	
Smoking	• Current	• Never or former	
Cigarette smoking:	• <1 to 10	• >10	
PGA:	• 3 to 4	• 5 to 6	
PASI:	• ≤ 15	• > 15	
CRP:	• <10 mg/dl	• ≥ 10 mg/dl	

The change in PASI and PGA will be evaluated utilizing following analyses:

- mean change from baseline in PASI by ANCOVA model
- location shift in change from baseline in PGA by Wilcoxon rank sum test and Hodges-Lehmann Estimation

If applicable, the analyses will be stratified by country.

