2 – Mild	XX (XXX.X%)	XX (XXX.X%)	XX (XXX.X%)
3 – Mild to moderate	XX (XXX.X%)	XX (XXX.X%)	XX (XXX.X%)
4 – Moderate	XX (XXX.X%)	XX (XXX.X%)	XX (XXX.X%)
5 – Moderate to severe	XX (XXX.X%)	XX (XXX.X%)	XX (XXX.X%)
6 – Severe	XX (XXX.X%)	XX (XXX.X%)	XX (XXX.X%)

Source data: <DATASET> <DATE>
Program: <SAS PROGRAM> <DATE>

Table 14.3.14: PGA – Frequency counts – LOCF (FAS)
(Part 2 of 2)

PGA	MP1032 300 mg bid (N = XX)	MP1032 150 mg bid (N = XX)	Placebo bid (N = XX)
Week 12 / EoT			
N	XX	XX	XX
0 – Clear	XX (XXX.X%)	XX (XXX.X%)	XX (XXX.X%)
1 – Almost clear	XX (XXX.X%)	XX (XXX.X%)	XX (XXX.X%)
2 – Mild	XX (XXX.X%)	XX (XXX.X%)	XX (XXX.X%)
3 – Mild to moderate	XX (XXX.X%)	XX (XXX.X%)	XX (XXX.X%)
4 – Moderate	XX (XXX.X%)	XX (XXX.X%)	XX (XXX.X%)
5 – Moderate to severe	XX (XXX.X%)	XX (XXX.X%)	XX (XXX.X%)
6 – Severe	XX (XXX.X%)	XX (XXX.X%)	XX (XXX.X%)
Week 16 / Follow-up			
N	XX	XX	XX
0 – Clear	XX (XXX.X%)	XX (XXX.X%)	XX (XXX.X%)
1 – Almost clear	XX (XXX.X%)	XX (XXX.X%)	XX (XXX.X%)
2 – Mild	XX (XXX.X%)	XX (XXX.X%)	XX (XXX.X%)
3 – Mild to moderate	XX (XXX.X%)	XX (XXX.X%)	XX (XXX.X%)
4 – Moderate	XX (XXX.X%)	XX (XXX.X%)	XX (XXX.X%)
5 – Moderate to severe	XX (XXX.X%)	XX (XXX.X%)	XX (XXX.X%)
6 – Severe	XX (XXX.X%)	XX (XXX.X%)	XX (XXX.X%)

Source data: <DATASET> <DATE>
Program: <SAS PROGRAM> <DATE>

Table 14.3.15: PGA – PGA improvement – LOCF (FAS)
Analog to Table 14.3.3 for PGA

Table 14.3.16: PGA – Descriptive statistics – LOCF (VCS)
Analog to Table 14.3.2 for PGA (VCS)

Table 14.3.17: PGA – Frequency counts – LOCF (VCS)
Analog to Table 14.3.14 for VCS

Table 14.3.18: PGA – PGA improvement – LOCF (VCS)
Analog to Table 14.3.3 for PGA (VCS)

Table 14.3.19: BSA [%] – Descriptive statistics – LOCF (FAS)
Analog to Table 14.3.2 for BSA score

Table 14.4.1: PASI – Subgroup: Analysis center – ANCOVA for change from baseline – LOCF (FAS)
Analog to Table 14.3.7 for Subgroups: Analysis centers (pooled): 1; 2; ...; [**<X>**](#).

Table 14.4.2: PASI – Subgroup: Age – ANCOVA for change from baseline – LOCF (FAS)
Analog to Table 14.3.7 for Subgroups: Age: 18 to 40; >40.

Table 14.4.3: PASI – Subgroup: Sex – ANCOVA for change from baseline – LOCF (FAS)
Analog to Table 14.3.7 for Subgroups: Sex: Male; Female.

Table 14.4.4: PASI – Subgroup: BMI – ANCOVA for change from baseline – LOCF (FAS)
Analog to Table 14.3.7 for Subgroups: BMI: Normal (≤ 24.9); Pre-obesity (25.0 - 29.9); Obesity (≥ 30.0).

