Table 14.4.5: PASI – Subgroup: Years of psoriasis – ANCOVA for change from baseline – LOCF (FAS)
Analog to Table 14.3.7 for Subgroups: Years of psoriasis: 1 to 10; >10.

Table 14.4.6: PASI – Subgroup: Smoking – ANCOVA for change from baseline – LOCF (FAS)
Analog to Table 14.3.7 for Subgroups: Smoking: Current; Never or former.

Table 14.4.7: PASI – Subgroup: Cigarette smoking – ANCOVA for change from baseline – LOCF (FAS)
Analog to Table 14.3.7 for Subgroups: Cigarette smoking: <1 to 10; >10.

Table 14.4.8: PASI – Subgroup: PGA – ANCOVA for change from baseline – LOCF (FAS)
Analog to Table 14.3.7 for Subgroups: PGA: 3 to 4; 5 to 6.

Table 14.4.9: PASI – Subgroup: PASI – ANCOVA for change from baseline – LOCF (FAS)
Analog to Table 14.3.7 for Subgroups: PASI: ≤ 15 ; > 15.

Table 14.4.10: PASI – Subgroup: CRP – ANCOVA for change from baseline – LOCF (FAS)
Analog to Table 14.3.7 for Subgroups: CRP: <10 mg/dl; ≥ 10 mg/dl.

Table 14.4.11: PASI – Subgroup: % Exposure – ANCOVA for change from baseline – LOCF (FAS)
Analog to Table 14.3.7 for Subgroups: % Exposure: < 80%; $\geq 80\%$.

Table 14.4.12: PGA – Subgroup: Analysis center – Location shift in change from baseline – LOCF (FAS)
(Part 1 of 2)

PGA changes from baseline Analysis center (pooled): 01	MP1032 300 mg bid (N = XX)	MP1032 150 mg bid (N = XX)	Placebo bid (N = XX)
Week 4			
N	XX	XX	XX
Mean ± SD	X.X ± X.X	X.X ± X.X	X.X ± X.X
Median	X.X	X.X	X.X
Min , max	X , X	X , X	X , X
Comparison vs Placebo			
Estimate ± SE ¹	X.X ± X.XX	X.X ± X.XX	--
95%-CI ¹	X.X , X.X	X.X , X.X	--
p-value ²	X.XXX	X.XXX	--
Week 8			
N	XX	XX	XX
Mean ± SD	X.X ± X.X	X.X ± X.X	X.X ± X.X
Median	X.X	X.X	X.X
Min , max	X , X	X , X	X , X
Comparison vs Placebo			
Estimate ± SE ¹	X.X ± X.XX	X.X ± X.XX	--
95%-CI ¹	X.X , X.X	X.X , X.X	--
p-value ²	X.XXX	X.XXX	--
Week 12 / EoT			
N	XX	XX	XX
Mean ± SD	X.X ± X.X	X.X ± X.X	X.X ± X.X
Median	X.X	X.X	X.X
Min , max	X , X	X , X	X , X
Comparison vs Placebo			
Estimate ± SE ¹	X.X ± X.XX	X.X ± X.XX	--
95%-CI ¹	X.X , X.X	X.X , X.X	--
p-value ²	X.XXX	X.XXX	--

¹ Estimates and confidence interval by Hodges-Lehmann estimation using location shift.

² Wilcoxon rank sum test.

Source data: <DATASET> <DATE>
Program: <SAS PROGRAM> <DATE>

Table 14.4.12: PGA – Subgroup: Analysis center – Location shift in change from baseline – LOCF (FAS)
(Part 2 of 2)

PGA changes from baseline Analysis center (pooled): 01	MP1032 300 mg bid (N = XX)	MP1032 150 mg bid (N = XX)	Placebo bid (N = XX)
Week 16 / Follow up			
N	XX	XX	XX

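### The SAP analyses nine baseline factors by separate within-level comparisons with placebo, but plans no estimate or test of whether the treatment effect differs between levels

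*SAP*

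**What the plan says.** The subgroup paragraph of SAP 3.4.6.2 states that the groups in Table 4 "will be evaluated with respect to the primary efficacy variables PASI and PGA for each post-baseline visit within the FAS". Table 4 lists pooled analysis centre and nine fixed factors: age, sex, BMI, years of psoriasis, smoking, cigarette smoking, PGA, PASI and CRP. Two methods are named: "mean change from baseline in PASI by ANCOVA model" and "location shift in change from baseline in PGA by Wilcoxon rank sum test and Hodges-Lehmann Estimation". A closing sentence allows stratification by country where applicable.

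The appendix shows the intended layout. Table 14.4.3, for example, is specified as "Analog to Table 14.3.7 for Subgroups: Sex: Male; Female". Table 14.3.7 gives an adjusted mean per arm and, for each dose against placebo, an estimate with SE, 95% CI and p-value at Weeks 4, 8, 12 and 16. The PGA shell (Table 14.4.12) has the same rows at the same four visits. The later PGA subgroup shells (14.4.13 to 14.4.22) are titled as location-shift tables but refer back to the ANCOVA shell 14.3.7. Either template carries one p-value per dose per visit.

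The ANCOVA contains treatment, pooled centre and the baseline value. SAP 3.4 uses two-sided tests without multiplicity adjustment and treats all p-values as descriptive. SAP 3.4.6.1 postulates no formal hypotheses.

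**The concern.** A subgroup effect is a difference in treatment effect between levels. The planned tables show the effect within each level but not that difference or its uncertainty. A reader comparing men with women sees two estimates and two p-values per dose, visit and outcome, and may be drawn to factors where one p-value is small and the other is not. As the check shows, that pattern is common when the drug works equally well in both levels, because each level has only part of the sample.

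This matters because the trial is a proof of concept whose subgroup tables could inform the population of a later study. Restricting that population because one level reached a threshold and the other did not would rest on no evidence that the levels differ. The primary and secondary analyses are not affected.

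**Working it through.** **1. Is there a between-level comparison anywhere?**
- ANCOVA (SAP 3.4.6.2; Table 14.3.7 footnote): treatment, pooled centre, baseline. No treatment-by-subgroup term.
- Wilcoxon/Hodges-Lehmann: applied inside each level. No contrast between levels.
- List of tables 14.4.1 to 14.4.22: no interaction table.
- Breslow-Day (SAP 3.4.6.2): homogeneity across pooled centres, on responder odds ratios. It covers neither the change scores nor the nine fixed factors.
- Stratification by country: an adjustment, not a comparison of levels.

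**2. Number of p-values**
- Levels: eight two-level factors and BMI with three, so 8 × 2 + 3 = 19.
- Post-baseline visits: 4. Outcomes: 2. Dose comparisons: 2 ("MP1032 300 mg bid and MP1032 150 mg bid, each vs. the placebo treatment").
- 19 × 4 × 2 × 2 = 304. Each pooled centre adds 4 × 2 × 2 = 16; the number of pooled centres is not stated.
- The % exposure subgroup, which appears only in the appendix, would add 2 × 16 = 32.
- With no drug effect, the expected number below 0.05 is 304 × 0.05 = 15.2, and below 0.10 it is 30.4. These expectations hold despite correlation, but the p-values are not 304 independent chances.

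**3. The plan's own power figure**

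SAP 2.2: 40 per group, rates 0.674 and 0.40, two-sided alpha 0.10, power 80%. With pooled variance under the null:
- Mean rate 0.537; √(2 × 0.537 × 0.463) = 0.705; √(0.674 × 0.326 + 0.40 × 0.60) = 0.678.
- z = (0.274 × √40 − 1.645 × 0.705) / 0.678 = 0.845, so power = 0.801. The figure reproduces.

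It applies to responder rates. The subgroup analyses use change scores, for which the documents give no SD or mean difference, so overall power is varied below.

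**4. One level significant, the other not, under a uniform effect**

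Let δ = z(1−α/2) + z(power) be the whole-trial signal. A level holding share f of the patients has signal δ√f and power p = Φ(δ√f − z) + Φ(−δ√f − z), with z = z(1−α/2). The two levels are separate patients, so P(exactly one significant) = p₁(1 − p₂) + p₂(1 − p₁).

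Example, alpha 0.05, 80% power, 50:50: δ = 1.960 + 0.842 = 2.802; δ√0.5 = 1.981; p = 0.508; result 2 × 0.508 × 0.492 = 0.500.

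| Overall power | 50:50, α 0.05 | 30:70, α 0.05 | 50:50, α 0.10 | 30:70, α 0.10 |
|---|---|---|---|---|
| 90% | 0.466 | 0.540 | 0.446 | 0.509 |
| 80% | 0.500 | 0.549 | 0.496 | 0.537 |
| 50% | 0.406 | 0.422 | 0.433 | 0.444 |
| 30% | 0.287 | 0.293 | 0.325 | 0.328 |
| No effect | 0.095 | 0.095 | 0.180 | 0.180 |

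Over 50–90% power the range is 0.406 to 0.549. A 90:10 split at the planning effect gives 62–69% (40 or 50 per arm, either alpha).

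**5. What an interaction test does in the same setting**

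In 4,000 simulated three-arm trials with a uniform effect, within-level p-values disagreed in 47–56% of cases. A treatment-by-subgroup term was significant in 4.5–4.7% at alpha 0.05 and 9.5–10.3% at alpha 0.10, which is close to nominal.

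**The case against.** The strongest reply is that the SAP never says a subgroup effect will be inferred from one small and one large p-value. The trial is exploratory and all p-values are descriptive. This stands: a reader might infer such a rule from the table layout, but the documents do not contain it. It does not supply the missing quantity, because a description of a subgroup effect also needs the difference between levels.

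A reader might also conclude that about half of the two-level subgroups will look subgroup-specific. The documents do not support that as a flat statement. It needs substantial power on change scores and moderately balanced splits, and neither is given. If cigarette smoking is defined only in smokers, its two levels do not add up to the FAS. With 30–50% smokers split evenly (assumed), 80% overall power and alpha 0.05, the figure for that factor is about 31–41%.

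Nor can every level be taken to have 25 or fewer patients per arm. With about 50 per arm, the larger level of a 30:70 split has about 35.

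It is also tempting to say that the PASI 10–20 entry range was itself picked from a subgroup result. Protocol sections 2 and 5.2 report Phase IIa response in that range but do not give it as the reason for the criterion.

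Finally, for PASI the between-level difference and its SE could be calculated from the reported estimates and SEs. That is true, but it leaves the key contrast to the reader. Low power of interaction tests is likewise a fair point; a wide interval is then the correct message.

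**Conclusion.** The point holds in a limited form. For the nine fixed baseline factors, the SAP plans 304 within-level p-values and no estimate or test of a difference in effect between levels. For centre, the only heterogeneity test is on responder odds ratios. That gap follows directly from the text and shells.

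The 41–55% figure is conditional on a uniform effect, 50–90% overall power on change scores, 50:50 or 30:70 splits, and a threshold of 0.05 or 0.10. Weaker effects lower it: to 29–33% at 30% power, and to 10% or 18% with none. Very uneven splits raise it. In every case, disagreement between within-level p-values is no evidence of a subgroup effect. The consequence is confined to interpretation of exploratory tables, and a better analysis is available at little cost.

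**What to change.** Amend SAP 3.4.6.2 and the Table 14.4 shells before unblinding:

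- **PASI, fixed factors.** For each of the nine, add one ANCOVA of PASI change at Week 12 on the whole FAS with treatment, subgroup, treatment-by-subgroup, pooled centre and baseline PASI. For each dose, report the between-level difference in effect with 95% CI and the interaction p-value. That is 9 × 2 = 18 interaction p-values; BMI, with three levels, has two differences per dose.
- **Cigarette smoking.** Fit the model in the patients for whom the variable is defined, and state who they are.
- **Centre.** Use a treatment-by-centre term without entering centre a second time.
- **PGA.** Keep Wilcoxon/Hodges-Lehmann within levels. Add an interaction estimate at Week 12 from a linear or ordinal model as a supplement (18 more p-values, 36 in total). Correct the template reference in the PGA shells.
- **Reading rule.** State that within-level p-values are not evidence of a difference between subgroups. Dropping them in favour of estimates with CIs is optional.

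The cost is SAP wording and a few extra outputs, with no new data, visits or patients. The interaction tests have low power at this sample size, and most will be inconclusive.
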